Clinical Trial objectives:	Primary objectives: To evaluate, in a modified Dumas-Scholtz psoriasis mini-zone test, the safety and efficacy of CD10367 solution at 1% and 3% after a three weeks treatment period of once daily application.		
Clinical Trial design:	Exploratory, single-centre, investigator blinded, randomized, controlled, intra-individual study (Dumas-scholtz design).		
Total number of subjects (Planned):	As a screen failure rate of approximately 40% percent is expected, approximately 40 subjects may have to be screened in order to obtain 24		
-	subjects randomized.		
Number of clinical trial centers (Planned):	1 site.		
Region(s) / country(ies) involved (Planned):	France		
Clinical trial duration:	The planned clinical trial duration (from FSFV to LSLV) is approximately 5 months.		
	The planned duration of recruitment (from FSFV to LSFV) is approximately 3.5 months.		
Duration of subject participation:	Clinical trial participation for each subject is approximately 9 weeks including screening period.		
Key Inclusion criteria	Adult male or female aged at least 18 and up to 70 years old inclusive at screening visit.		
	Female of non-childbearing potential (postmenopausal [absence of menstrual bleeding for 1 year prior to screening, without any		

Protocol No.: RD.03.SPR.112075 V01 16 Aug 2016

Page 11 of 85

SYNOPSIS Clinical Trial Title: EXPLORATORY STUDY TO EVALUATE THE SAFETY AND EFFICACY OF CD10367 IN SUBJECTS WITH PSORIASIS				
				other medical reason], hysterectomy or bilateral oophorectomy).
				Subject has a skin phototype I to IV on Fitzpatrick's scale. (Screening visit).
	 The subject has a clinical diagnosis of stable plaque psoriasis, defined as no flare during the month before Screening visit and no change between Screening visit and Baseline visit, of mild to moderate severity. (Screening visit and Baseline Visit). 			
	 The subject presents with at least six eligible mini-zones, on at least two psoriasis plaques (Screening visit and verified also at Baseline Visit) with specific severity grades defined in the protocol (Screening and Baseline Visit) 			
	Subject agrees not to wear his/her contact lenses from the Baseline visit till the D19 visit,			
Key Exclusion criteria	The subject presents guttate, erythrodermic, exfoliative, inverse, pustular, palmo plantar, infected or ulcerated psoriasis (Screening visit).			
	 Any uncontrolled or serious disease, or any medical or surgical condition, that may either interfere with the interpretation of the clinical trial results, and/or put the subject at significant risk (according to Investigator's judgment) if he/she participates in the clinical trial (e.g. history of on-going gastric or duodenal ulcer, clinically significant lung disease, etc.). 			
	 Known or suspected allergies or sensitivities to any components of the study drugs or of the keratolytic product (see Investigator's Brochure/Product label). 			
	Subject with known history of adverse drug reaction or hypersensitivity to a product with the same mode of action			
	 Subject with any abnormal clinically significant findings according to the ophthalmologist, at the ophthalmological exam at Screening, 			
	 The subject presents any abnormal laboratory tests defined in the protocol (blood sampling and urinalysis done at Screening visit), 			
	QTc interval >450msec or any abnormal ECG value considered as clinically significant by the cardiologist at Screening,			
	The subject has received, applied or taken specific treatments within the time frame defined in the protocol prior to the Baseline			

Protocol No.: RD.03.SPR.112075 V01 16 Aug 2016

Page 12 of 85

	SYNOPSIS	
Clinical Trial Title: EXPLORATORY STUDY TO EVALUATE THE SAFETY AND EFFICACY OF CD10367 IN SUBJECTS WITH PSORIASIS		
OD 10307 IN OODSECTO WIT	visit.	
	viole.	
Investigational product:	NA	
Name:	NA	
Internal code [if applicable]:	CD10367	
Pharmaceutical form:	Solution	
[Strength/Concentration]:	1%	
Dosage (total daily dose):	50µl	
Route:	Topical	
Duration of administration:	Five consecutive days a week for two weeks and four consecutive days in the third week (14 applications)	
Dose regimen:	Once daily	
Location of treated area:	Mini-zones on upper and/or the lower extremities (elbows, knees and shin area excluded) and/or on the trunk	
Investigational product:	NA	
Name:	NA	
Internal code [if applicable]:	CD10367	
Pharmaceutical form:	Solution	
[Strength/Concentration]:	3%	
Dosage (total daily dose):	100μl (50μl on each mini-zone)	
Route:	Topical	
Duration of administration:	Five consecutive days a week for two weeks and four consecutive days in the third week (14 applications)	
Dose regimen:	Once daily	
Location of treated area:	Mini-zones on upper and/or the lower extremities (elbows, knees and shin area excluded) and/or on the trunk	
Investigational product:	NA	
Name:	NA	
Internal code [if applicable]:	CD10367 placebo	
Pharmaceutical form:	Solution	
[Strength/Concentration]:	NA	
Dosage (total daily dose):	100μl (50μl on each mini-zone)	
Route:	Topical	
Duration of administration:	Five consecutive days a week for two weeks and four consecutive days in the third week (14 applications)	
Dose regimen:	Once daily	
Location of treated area:	Mini-zones on upper and/or the lower extremities (elbows, knees and	

Protocol No.: RD.03.SPR.112075 V01 16 Aug 2016 Page 13 of 85

	SYNOPSIS	
Clinical Trial Title: EXPLORATORY STUDY TO EVALUATE THE SAFETY AND EFFICACY OF		
CD10367 IN SUBJECTS WIT		
	shin area excluded) and/or on the trunk	
Comparator:	Betneval	
Name:	Betamethasone valerate 0.1%	
Internal code:	NA	
Pharmaceutical form:	Ointment	
[Strength/Concentration]:	0.1%	
Dosage (total daily dose):	50µl	
Route:	Topical	
Duration of	Five consecutive days a week for two weeks and four consecutive days	
administration:	in the third week (14 applications)	
Dose regimen:	Once daily	
Location of treated area:	Mini-zones on upper and/or the lower extremities (elbows, knees and shin area excluded) and/or on the trunk	
Efficacy assessment:	The individual scores and clearing scores will be assessed twice weekly by the investigator.	
		
Efficacy endpoints:	Primary efficacy endpoint(s) or co-primary endpoint(s)	
	Area Under the Curve (AUC) of Total Sum Score (sum of erythema, scaling and induration scores) from Day 1 to Day 19.	
	Secondary efficacy endpoint(s)	
	AUC of individual clinical scores (erythema, scaling and induration) from Day 1 to Day 19.	
	TSS and percentage change from baseline at each visit.	
	Erythema, Scaling and Induration score and their change from baseline at each visit.	
	Success rate (defined as a clearing score of 0 or 1) at each evaluation visit and the time to first success.	
Safety assessment:	A safety assessment will be conducted for all subjects at screening visit (from the Informed consent signature) and every subsequent visit.	
Safety endpoints [only when applicable]:	Local tolerance assessed twice weekly by the Investigator using a 4-point scale for each mini-zone	
	 Physical examination at Screening, and Day 19 (or Early Termination visit if any); 	
	 Record of vital signs at Screening, Baseline and Day 19 (or Early Termination visit if any); 	
	1	

Protocol No.: RD.03.SPR.112075 V01 16 Aug 2016 Page 14 of 85

SYNOPSIS						
Clinical Trial Title: EXPLORA CD10367 IN SUBJECTS WITH	TORY STUDY TO EVALUATE THE SAFETY AND EFFICACY OF PSORIASIS					
	Termination visit if any);					
	• ECG at Screening, and Day 19 (or Early Termination visit if any);					
	 Blood samplings for laboratory safety tests at Screening and Day 19 (or Early Termination visit if any); 					
	 Urinalysis at Screening and Day 19 (or Early Termination visit if any); 					
	 Monitoring and recording of AEs to be recorded as specified in Section 7.2.6. 					
CCI						
Sample size:	CCI					

[figure not shown]
Protocol No.: RD.03.SPR.112075 V01 16 Aug 2016 Page 15 of 85

SYNOPSIS					
Clinical Trial Title: EXPLORATORY STUDY TO EVALUATE THE SAFETY AND EFFICACY OF CD10367 IN SUBJECTS WITH PSORIASIS					
	Therefore 24 subjects are planned to be randomized.				
	This sample size is sufficient to assess also local tolerance in standard tolerance topical studies.				

Protocol No.: RD.03.SPR.112075 V01 16 Aug 2016

GALDERMA R&D

Table 1 Clinical trial schematic

Protocol No.: RD.03.SPR.112075 V01 16 Aug 2016

Page 17 of 85

 Table 2
 Schedule of Assessments

	Screening period	Pre-treatment period	Treatment Period								Follow-up period			
	Up to 3 weeks before pre-treatment period	1 or 2 weeks a before treatment period	Week 1			Week 2			Week 3		Week 4 to 5			
			D1	D2 &D3	D4	D5	D8	D9 & D10	D11	D12	D15	D16&D17&D18	Final visit D19 /ET	D26 +/- 2
Informed Consent Form	X													
Demographics and Medical history	Х													
Previous treatments and procedures	X													
Physical examination	Х												Х	
Vital signs	Х		Х										Х	
ECG	>	(b											Х	
Ophthalmic examination	>	(b											Х	
Inclusion Criteria and Exclusion Criteria	Х		Х											
Selection of target sites	Х		Х											
Urinalysis	Х												Х	
Safety tests Blood sampling	Х												Х	
Randomization			Х											
Local Tolerance c				D2 only	Χ		Χ		Х		Χ		Х	
Individual clinical scores	Х		Х		Χ		Χ		Х		Χ		Х	
Clearing score					Χ		Χ		Х		Х		Х	
Keratolytic product application of selected plaque at home daily		X												
Products application			Х	Х	Χ	Χ	Χ	Х	Х	Х	Х	X		
CCI														
PK blood sampling						Χ							Х	Х
CCI														
Concomitant treatments and Procedures	X	X	Χ	Х	Χ	Χ	Χ	Х	Χ	Χ	Χ	Х	Х	Х
Adverse events d	Х	X	Х	Х	Χ	Χ	Χ	Х	Х	Х	Х	Х	Х	Х
Exit form e													Χf	Х

a. if the scaling score did not reach 0 or 1 after 1 week of pre-treatment, the pre-treatment period can be extended to 2 weeks, otherwise the subjects will start D1 visit immediately. b ECG and ophthalmic exams should be done as close as possible to baseline visit. c Local tolerance of the concerned zone must be taken at any visit in case of AE in a treatment zone. d Adverse Events have to be collected from the ICF signature. e Exit form should be signed after subject data collection has been completed. f Exit form should be completed at ET visit only if no follow-up visit is planned (discontinuation)

Protocol No.: RD.03.SPR.112075 V01 16 Aug 2016

Page 18 of 85

LIST OF ABBREVIATIONS AND DEFINITIONS OF TERMS

Abbreviation	Term	
ACE	Angiotensin-converting-enzyme	
AE	Adverse Event	
AESI	Adverse Event of Special Interest	
ALP	Alkaline Phosphatase	
ALT/ALAT (SGPT)	Alanine Aminotransferase (Serum Glutamic Pyruvic Transaminase)	
AST/ASAT (SGOT)	Aspartate Aminotransferase (Serum Glutamic Oxaloacetic Transaminase)	
AUC	Area under Curve	
AZ	AstraZeneca	
BID	Twice Daily (Latin: bis in die)	
CA	Competent Authorities	
CRA	Clinical Research Associate	
CRF/eCRF	Case Report Forms/electronic Case Report Forms	
CRO	Contract Research Organization	
CSO	Clinical Safety Officer	
DMP	Data Management Plan	
DS	Drug substance	
ECG	Electrocardiogram	

Protocol No.: RD.03.SPR.112075 V01 16 Aug 2016 Page 19 of 85

Abbreviation	Тегт
e.g.	For Example (Latin: exempli gratia)
CCI	
CCI	
CCI	
CCI	
ET	Early Termination
etc	Et cetera
EU	European Union
FDA	Food and Drug Administration
FSFV	First Subject First Visit (date of first subject included i.e., informed consent signature)
GCP	Good Clinical Practice
GLP	Good laboratory practice
GRD	GALDERMA R&D
Hb	Hemoglobin
HBsAg	Hepatitis B Surface Antigen
Het	Hematocrit
HCV	Hepatitis C Virus
HIV	Human Immunodeficiency Virus

Protocol No.: RD.03.SPR.112075 V01 16 Aug 2016 Page 20 of 85

Abbreviation	Term	
IB	Investigator's Brochure	
ICF	Informed consent form	
ICH	International Conference on Harmonisation	
ID	Identity	
i.e.	That is (Latin: id est)	
IEC	Independent Ethics Committee	
IHC	immunohistochemistry	
IL	Interleukin	
IMP	Investigational medicinal product	
IRB	Institutional Review Board	
ITT	Intent-to-treat	
LOCF	Last Observation Carried Forward	
LOQ	Limit of Quantification	
LSFV	Last Subject First Visit (date of last subject included i.e., informed consent signature)	
LSLV	Last Subject Last Visit (date of last subject's last study visit)	
MALDI-FTICR-MS	Matrix Assisted Laser Desorption Ionization	
MCV	mean cell volume	
MD	Medical Doctor	

Protocol No.: RD.03.SPR.112075 V01 16 Aug 2016 Page 21 of 85

Abbreviation	Term			
ME ME	Medical Expert			
MedDRA	Medical Dictionary for Regulatory Activities			
mL	Milliliter			
N or n	Number			
N/A	Not Applicable			
NOAEL	No-observed-adverse-effect level			
CCI				
OTC	Over-the-counter			
p	Page(s)			
CCI				
PE	Physical Examination			
CCI				
PK	Pharmacokinetics			
Plt	Platelets			
PO	Per os (Oral administration)			
PP	Per-Protocol			
PT	Preferred terms			
QD	Once Daily (Latin: quaque die)			
RBC	Red blood cell			

Protocol No.: RD.03.SPR.112075 V01 16 Aug 2016 Page 22 of 85

Abbreviation	Term	
SAE	Serious Adverse Event	
SAP	Statistical Analysis Plan	
SD	Standard Deviation	
SOC	System Organ Class	
SOP	Standard Operating Procedure	
SUSAR	Suspected Unexpected Serious Adverse Reaction	
TEAE	Treatment-emergent Adverse Event	
TESS	Treatment Emergent Signs and Symptoms	
TOC	Table of Contents	
TSS	Total Sum Score	
UA	Urinalysis	
ULN	Upper Limit of Normal	
UV	ultraviolet	
WBC	White Blood Cell	

Protocol No.: RD.03.SPR.112075 V01 16 Aug 2016

Page 23 of 85

1 BACKGROUND AND RATIONALE

1.1 Medical background and Short rationale for the clinical trial

1.2 Psoriasis

Psoriasis is a common, genetically determined, inflammatory and proliferative disease of the skin affecting 1.5% to 3% of the general population. The most characteristic lesions consist of chronic, sharply demarcated, dull-red scaly plaques, particularly on extensor parts of limbs. It can affect any body area including the face, palms, soles, folds, scalp and nails leading to erythema, scaling and thickening of the skin.

Genetic-environmental interaction is usually considered for the causation of psoriasis. Smoking, alcohol consumption, diet, psychological stress, infections and physical trauma have been suggested as factors which may influence the onset of the disease and/or may affect severity or the response to treatment.

The clinical course is unpredictable but in the majority of cases psoriasis is a chronically remitting and relapsing disease. Chronic stable plaque psoriasis (*psoriasis vulgaris*) is the most common form of the disease, accounting for 85% to 90% of cases. The circumscribed infiltrated skin lesions are scaly and erythematous and often symmetrically distributed over the body. Most of the patients suffer from mild to moderate plaque psoriasis with a body surface involvement of less than 10%. The majority of these patients can be treated with topical treatments, which generally provide both efficacy and safety (Menter et al., 2007).

Psoriasis principal histological features are: thickening of the epidermis, parakeratosis, elongated rete ridges, and a mixed cellular infiltrate in the dermis (Griffiths and Barker, 2007). The inflammatory infiltrate consists mainly in the dermis of dendritic cells, mast cells, macrophages, natural killer cells and different T-cell types such as CD4+ helper cells, CD8+ cytotoxic cells (Jullien, 2006).

Keratinocytic hyperproliferation is mediated by pro-inflammatory cytokines produced by T-cells and dendritic cells that accumulate in diseased skin. Several inflammatory cytokines (e.g. interleukin 1 (IL-1), IL-6, IL-8, interferon- γ , and tumor necrosis factor- α (TNF- α)) are known to trigger epidermal hyperplasia through direct or indirect pathways (Jullien, 2006).

Although there is no cure for psoriasis, a variety of treatments is available to reduce the severity of symptoms and lessen their impact on the patient's quality of life.

For patients with less than 20% body surface involvement, topical therapy is the most appropriate choice for the initial treatment. Commonly used topical therapies include corticosteroids, calcipotriol (a vitamin D analogue), tazarotene (the first topical retinoid approved for the treatment of psoriasis) and anthralin. Each of these treatments is effective in mild to moderate psoriasis, but each is also associated with varying degrees of safety and tolerability concerns.

[figure not shown]
Protocol No.: RD.03.SPR.112075 V01 16 Aug 2016

Page 24 of 85

For patients with more severe, recalcitrant, or extensive psoriasis, phototherapy and systemic therapies are available. These therapies are more effective than topical therapy, but are also associated with significant cutaneous and systemic adverse effects.

Epidermal growth factor receptor (EGFR) is normally expressed in the skin, primarily in the proliferating undifferentiated keratinocytes of the basal cell layers of the epidermis and plays a key role in cellular proliferation, survival and differentiation. EGFR over-expression or overactivity was associated with a number of cancers (e.g. lung, anal, head and neck, etc), but recent data also showed an overexpression of EGFR ligands in lesional psoriasis skin (Johnston et al, 2011). Varani et al showed in an in vitro study that psoriatic plaque skin incubated for eight days in the presence of a potent EGFR tyrosine kinase antagonist reverted to a normal histological appearance (Varani et al, 2005).

There are also several case reports of patients with cancer treated by EGFR inhibitors showing an improvement of their psoriasis (Overbeck and Griesinger, 2012).

Therefore the purpose of this study is to evaluate the safety, efficacy, collection of CD10367 topical solution in psoriasis.

1.3 Drug profile

CD10367 is a potent and selective inhibitor of the tyrosine-kinase domain of the epidermal growth factor receptor (EGFR-TKI). This compound was initially developed as an oral formulation by AstraZeneca (AZ) for the treatment of solid tumors (including non-small cell lung cancer).

The compound is currently evaluated by GALDERMA R&D for the topical treatment of several indications such as psoriasis.

1.4 Risk/Benefit assessment

This is an exploratory study to evaluate on psoriasis mini-zones the safety, efficacy, of CD10367 topical solution at 1% and 3%. As only mini-zones will be treated in this study no individual benefit is expected for the subjects who will participate to the study.

Protocol No.: RD.03.SPR.112075 V01 16 Aug 2016

Page 25 of 85

All investigational medicinal product (IMP) will be applied on mini-zones, located on psoriatic plaques, and the quantity applied will be under the control of the qualified staff who will perform all the applications at the site and no IMP will be given to the subjects for applications at home.

In order to improve the drug penetration, in this study, one or two psoriasis plaque(s) will be desquamated using a marketed cosmetic keratolytic agent containing urea and low concentration of salicylic acid prior to application of CD10367 and its placebo on mini-zones. In clinical practice, urea and salicylic acid-based products are usually associated with local psoriasis treatments in order to increase and fasten their efficacy. Only mild irritation has been reported as the most common side effect, making urea a safe and well-tolerated topical drug (Pan, 2013; Jacobi, 2015). This keratolytic product will be applied twice daily by the subjects at home.

The safety ratios calculation for the current study were estimated using two approaches: 1) in accordance with regulatory guidance (FDA Guidance for Industry July 2005), CCI

CCI		

Protocol No.: RD.03.SPR.112075 V01 16 Aug 2016

Page 26 of 85

Considering the estimated safety ratios for the proposed study and the short treatment duration, these safety risks are not expected to occur. However, appropriate inclusion/ exclusion criteria and safety follow-up measures have been planned.

Regarding the ocular toxicity risk, even if clinical studies done by AZ and GRD did not confirm this risk in human being, specific inclusion/exclusion criteria have been defined to minimize this risk for the subjects, e.g. exclusion of subjects with abnormal ophthalmic examination according to the ophthalmologist at Screening, etc.

As to the cardiac risk, an ECG is planned at screening with exclusion of subjects with any clinically significant ECG findings; an ECG monitoring is planned during the study.

Other toxicities have been reported for marketed oral or injectable EGFR inhibitors such as acneiform skin rash, gastrointestinal side effects (diarrhea), interstitial lung disease, hepatotoxicity or renal toxicity (MacDonald JB et al. 2015, Gillespie et al. 2009).

As mentioned above for the ocular toxicity risk and the cardiac risk, these potential reactions are not expected to occur in the proposed study, considering the limited quantity of product applied and the short treatment duration.

During the study, subjects safety will be closely monitored on a daily basis during product application period and at the follow-up visit taking into account data generated during the development of the oral route by AZ and the GRD studies for the topical route.

Protocol No.: RD.03.SPR.112075 V01 16 Aug 2016

Page 27 of 85

Local tolerance during the drug application period will be assessed systematically in order to evaluate any potential irritancy, sensitization reaction or papulo-pustular eruption.

In conclusion, based on the current non-clinical and clinical data presented above and detailed in the Investigator's Brochure, CCI , the Sponsor considers that CD10367 topical solution at 1% and 3% does not raise any safety concerns when applied under the defined clinical study conditions.

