7.2.5 Local tolerability assessment

Local tolerability assessment will be performed using the following twice a week from Day2 to Day 19/ET visits scales two times per week during the treatment period. If at any visit, a treatment leads to discontinue applications either temporarily or permanently, an AE must be declared, and local tolerability assessments and photos of the concerned zone must be performed even if it was not planned in study flowchart for this visit. Grading for local tolerability assessments will take into consideration the time period from the last local tolerability assessment up to the current visit. The worst severity since the previous visit will be recorded. Local tolerability (Irritation, stinging/burning, pruritus) will be assessed separately on each minizone using the following scales:

Protocol No.: RD.03.SPR.112075 V01 16 Aug 2016

Page 52 of 85

Table 7 Local tolerance 4-point scales

Irritation	Skin irritati	n Assessment						
0	None:	o signs of irritation						
1	Mild:	Slight signs of irritation						
2	Moderate:	Moderate signs of irritation: Obvious increase in redness as compared to the non-treated surrounding area						
3	Severe:	Severe signs of irritation						
Stinging/ Burning	Prickling p	ain sensation						
0	None:	No stinging/burning						
1	Mild:	Slight warm, tingling/stinging sensation; not really bothersome						
2	Moderate:	Definite warm, tingling/stinging sensation that is somewhat bothersome						
3	Severe:	Hot, tingling/stinging sensation that causes severe discomfort						
Pruritus	Itch sensat	tion						
0	None:	No itching						
1	Mild:	Itching is noticeable but not really bothersome						
2	Moderate:	Definite itching that is somewhat bothersome						
3	Severe:	Marked itching, urge to scratch and causes definite discomfort						

Irritation, will be clinically evaluated by the Investigator. The Investigator will record stinging/burning and pruritus after discussion with the subject. The severity of stinging/burning sensation occurring after the last drug application before the visit will be asked. The Investigator will ask an open-ended question, taking care not to influence the subject's answer, such as "Have you experienced any sensations such as stinging/burning?"

An Adverse Event page must be completed if the severity of the signs and symptoms is such that:

- The subject temporary or permanently discontinues the treatment at his/her request or at the Investigator's request.

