- The subject requires concomitant treatment, including OTC products (other than moisturizer).

In case of permanent treatment discontinuation, skin sensitization or papulo-pustular reaction an AESI must be declared (see section 7.2.6.1.3).

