7.2.6.1.3 Adverse Events of Special Interest (AESIs)

An AESI is a noteworthy event for the particular study drug that can be appropriate to monitor closely. It could be serious or non-serious and AESIs could include events that might be potential precursors or prodromal symptoms for more serious medical conditions in susceptible individuals.

The AESIs for this protocol have been pre-defined as follows:

- Suspected sensitization or photosensitization
- Any non-dermatological treatment-emergent related adverse events (AE), including:
 - Increase in QTc interval from Baseline >60msec or a value>500msec at D19/ET ECG assessed as related to the study drug
 - Out-of-range laboratory results that are identified as both clinically significant and related to the study drug(s)
 - Any treatment-emergent signs/symptoms suggestive of keratitis or corneal ulceration (e.g. pain of the eye, injected/red eye, blurred vision, etc.), or treatment-emergent keratitis or corneal ulceration diagnosed at the ophthalmological examination, or any other treatment-emergent acute ophthalmological findings assessed as related to the study drug
- Any dermatological treatment-emergent related adverse events (AE) leading to permanent treatment discontinuation on any zone
- Treatment-emergent skin rash assessed as related to the study drug, defined as a papulopustular eruption commonly described as acneiform eruption

For AESIs, the Investigator is required to complete the Adverse Event Form on the CRF and follow the AESI reporting procedures in Section 7.2.6.2.3 even if the event is considered non-serious according to the usual regulatory criteria.

Protocol No.: RD.03.SPR.112075 V01 16 Aug 2016

Page 55 of 85

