9.1.3 Data presentation and graphics

The subject disposition, demographics, baseline characteristics, previous therapies, concomitant therapies will be summarized by descriptive statistics.

All efficacy variables will also be summarized by treatment (treatment / pre-treatment) at each visit. The categorical variables will be summarized by frequency and percentage for each response category (N, %). The continuous variables will be summarized using means, medians, minimum, maximum, and standard deviations for the data collected at each visit.

The area under the curve of the TSS (sum of individual clinical scores erythema, induration/plaque elevation and scaling), as well as those of each individual clinical score will be calculated from Day 1 (before application) up to Day 19 by subject and by treatment, using the trapezoidal rule.

The time to success (defined as a clearing score of 0 or 1) will be summarized by treatment. Only the earliest day of success will be considered in defining the time to partial clearing, independently of the subsequent days.

The local tolerance scores will be summarized using frequency and percentage by visit and study product. The worst scores will also be summarized.

Adverse Events will be tabulated by study treatment. Adverse Events will be tabulated in frequency tables by System Organ Class (SOC) and Preferred Term (PT) based on the MedDRA dictionary. Additional summary tables will be provided for Adverse Events that will be considered as severe, serious (SAEs) and Adverse Events leading to discontinuation. Any AE and related AE will be summarized for each category. Analyses of adverse events will be based on Treatment Emergent Signs and Symptoms (TESS) *i.e.* adverse events occurring on the day of, or after, treatment application (Baseline).

Events having occurred before the day of treatment application (i.e. before Baseline) will be listed only.

Due to the intra-individual study design and whenever possible (known from e-CRF), AE will be imputed to the treated area, when not possible then the AE will be imputed to all treated area.

Physical examination, vital signs, ECG and ophthalmic examination will be summarized by descriptive statistics.

Shift tables for the laboratory data (and urinalysis) will be tabulated for each laboratory parameter.

Protocol No.: RD.03.SPR.112075 V01 16 Aug 2016

Page 75 of 85

Pharmacokinetics parameters will be descriptively summarized.

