4.2. Safety variables

- Local tolerance (irritation, stinging/burning, pruritus) twice weekly using a 4-point scale for each mini-zone:

Irritation	Skin irritati	Skin irritation Assessment						
0	None:	No signs of irritation						
1	Mild:	Slight signs of irritation						
2	Moderate:	Adderate signs of irritation: Obvious increase in redness as compared to the on-treated surrounding area						
3	Severe:	Severe signs of irritation						
Stinging/ Burning	Prickling pa	ling pain sensation						
0	None:	No stinging/burning						
1	Mild:	Slight warm, tingling/stinging sensation; not really bothersome						
2	Moderate:	Definite warm, tingling/stinging sensation that is somewhat bothersome						
3	Severe:	Hot, tingling/stinging sensation that causes severe discomfort						
Pruritus	Itch sensatio)n						
0	None:	No itching						
1	Mild:	Itching is noticeable but not really bothersome						

2	Moderate:	Definite itching that is somewhat bothersome
3	Severe:	Marked itching, urge to scratch and causes definite discomfort

- Incidence and multiplicity of Adverse Events (from informed consent signature to the end of the study);
- Ophtalmic examination at screening and day 19/ET
- Physical examination at screening and day 19/ET;
- Vital signs performed after 5 minutes rest in the sitting position (systolic blood pressure, diastolic blood pressure, pulse rate, vital signs evaluation) at screening, baseline and day 19/ET;
- 12-lead electrocardiogram during the screening period and at day 19/ET;
- Blood samplings for laboratory safety tests (haematology and blood chemistry) at screening and day 19/ET (Virology will be performed only at screening);
- Urinalysis at screening and day 19/ET;

CC

5. **POPULATIONS ANALYZED**

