7.3.2. Local tolerance

Local individual signs/symptoms (irritation, skinging/burning, pruritus) in term of frequency distribution and in quantitative description and the worst score (from Day 2 to Day 19/ET) over time of each individual sign/symptom will be calculated by study product.

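### Section 1.4 of the protocol promises systematic evaluation of papulo-pustular eruption, but the visible per-zone tolerance scales have no such item and the reaction is captured only as an event-driven AESI

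*Protocol*

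**What the plan says.** Protocol Section 1.4 identifies the class risk: "Other toxicities have been reported for marketed oral or injectable EGFR inhibitors such as acneiform skin rash". It regards these reactions as unexpected here, given the small quantity applied and the short treatment. It then sets out the local monitoring: "Local tolerance during the drug application period will be assessed systematically in order to evaluate any potential irritancy, sensitization reaction or papulo-pustular eruption".

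The instrument is in protocol 7.2.5: "Local tolerability (Irritation, stinging/burning, pruritus) will be assessed separately on each minizone using the following scales". Table 7 has those three items, each graded 0 to 3. SAP 4.2 repeats them: "Local tolerance (irritation, stinging/burning, pruritus) twice weekly using a 4-point scale for each mini-zone". SAP 7.3.2 analyses the same three: "Local individual signs/symptoms (irritation, skinging/burning, pruritus) in term of frequency distribution and in quantitative description", plus the worst score by product. The table shells in SAP 9.3.2 and the tolerance graphs in SAP 9.4 follow suit.

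The reaction has a separate route. Protocol 7.2.5 ends with: "In case of permanent treatment discontinuation, skin sensitization or papulo-pustular reaction an AESI must be declared". The AESI list in 7.2.6.1.3 contains: "Treatment-emergent skin rash assessed as related to the study drug, defined as a papulopustular eruption commonly described as acneiform eruption". On allocation to zones, protocol 9.1.3 says that, whenever possible, "AE will be imputed to the treated area, when not possible then the AE will be imputed to all treated area". SAP 7.3.3 has the same rule and tabulates events by treatment/pre-treatment, and SAP 9.3.3 plans an AESI table.

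**The concern.** The risk section presents scheduled local tolerance assessment as the means of evaluating papulo-pustular eruption, but the scoring form has nowhere to record it. Safety is part of the primary objective, and good tolerability is part of the clinical hypothesis (protocol 2.1 and 2.2). The intra-individual design exists to compare products zone by zone. For the local skin sign that the protocol itself links to this drug class, that comparison would rest on events that someone chose to report. With event-driven capture, no report can mean either that the zone was examined and clear or that the sign was not noted. Only a scheduled item separates the two.

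**Working it through.** The documents give no figure to reproduce. The check sets the passages side by side and adds two short calculations.

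**1. Promise against instrument.** Section 1.4 names three targets.

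| Target in 1.4 | Item in Table 7 / SAP 4.2 / SAP 7.3.2 | Other route |
|---|---|---|
| Irritancy | Yes (irritation, 0–3) | AE if treatment is stopped or concomitant treatment is needed |
| Sensitization | No | AESI, with re-challenge procedure (7.2.6.2.3.1) |
| Papulo-pustular eruption | No | AESI (7.2.5, 7.2.6.1.3) |

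Stinging/burning and pruritus are symptoms and do not stand in for the missing sign. Grade 1 irritation is defined only by slight signs, with no morphology.

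**2. Size of the scheduled opportunity.** Table 2 and Sections 8.1.3 and 8.1.4 place tolerance scoring on Days 2, 4, 8, 11, 15 and 19, which is 6 visits.
- Per subject: 6 zones × 6 visits × 3 items = 108 planned scores, none for papules or pustules.
- Whole trial: 24 subjects × 6 zones × 6 visits = 864 planned zone-visit examinations.

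**3. What the AESI route can estimate.** Each subject receives all six conditions, so if all 24 are treated the denominator is 24 per condition (safety population, SAP 5.3). For zero reported events the exact upper limits are:
- one-sided 95%: 1 − 0.05^(1/24) = 11.7%
- two-sided 95%: 1 − 0.025^(1/24) = 14.2%

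These limits would be the same for 0/24 from a scheduled item, so they do not measure what the item adds. The difference is ascertainment. If the event route detects a fraction *s* of true reactions, 11.7% bounds the reported rate and the one-sided bound on the true rate is 11.7%/*s*. The documents give no value for *s*, and I assume none.

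**4. Events that cannot be placed.** Let *a* events be placed on a CD10367 zone and *b* on its placebo zone, with *u* events that cannot be placed. Under the imputation rule the counts are *a* + *u* and *b* + *u*. The difference is *a* − *b*: the unplaced events raise both rates and contribute nothing to the contrast.

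**5. What must be declared.** The sentence in 7.2.5 covers a papulo-pustular reaction with no condition on relatedness. The entry in 7.2.6.1.3 covers only rash judged related to the study drug. The reporting procedure in 7.2.6.2.3 applies to AESIs whether related or not, but refers back to the 7.2.6.1.3 list. The number of AESIs therefore depends on which passage the site follows.

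**The case against.** The best defence is that 1.4 and 7.2.5 can be read as coherent. Zones are examined at scheduled visits, graded signs are scored, and discrete reactions are declared as AESIs. Sensitization, named in the same sentence of 1.4, is handled in the same way. Section 1.4 promises systematic assessment of local tolerance; it does not say that each target has its own graded item. Nor is capture passive: adverse events are sought on each of the five weekly treatment days (3.2.9), directed questioning and examination follow as appropriate (7.2.6.2.1), efficacy is scored by dermatologists (7.6), and an adverse event in a zone triggers a tolerance assessment of that zone (Table 2, note c). A local eruption is also among the easiest events to place.

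Much of this stands. A reader might infer that the trial will have no data by zone on this reaction, that no rate by product or against vehicle can be given, or that no denominator exists. The documents do not support that: zone attribution, tabulation by treatment, an AESI table and a safety population are all planned. A reader might also infer that mild papules will be graded as slight irritation and lost. That could happen, but 7.2.5 requires an AESI for a papulo-pustular reaction whatever the irritation grade, so it cannot be asserted.

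The defence does not turn event-driven capture into a scheduled record. The daily enquiry starts with an open question to the subject, and subjects are told not to remove the bandages on treated zones (8.2), so a visible sign may escape them. The investigator's scheduled inspection is the natural detector, and its visible form has no field for the finding.

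**Conclusion.** The point holds in limited form. The visible tolerance scales do not deliver by scheduled scoring what Section 1.4 says tolerance assessment is for. Papulo-pustular reaction will yield a reported-event rate by product, not a rate from planned examination of each zone. Under 7.2.6.1.3, though not under 7.2.5, the count is further filtered by a relatedness judgement. The comparison with vehicle is weaker than a scheduled record would give, by an amount the documents do not let us calculate.

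The efficacy analysis is unaffected. The conclusion assumes that the unredacted scales and SAP outputs are complete for tolerance scoring. Parts of the schedule and of the safety analysis are redacted, and 7.2.5 mentions photographs of affected zones, so scheduled photographs or other records may add information by zone. I count that neither for nor against the plan.

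**What to change.** - Add one papules/pustules item per zone to Table 7 and the CRF at the existing tolerance visits (Days 2, 4, 8, 11, 15 and 19), as absent/present or as an anchored none/few/many scale. Record it irrespective of judged relatedness.
- Add the item to SAP 4.2 and 7.3.2, summarised by visit and as worst score by product, with a matching shell in SAP 9.3.2.
- Keep the AESI route alongside it.
- Reconcile protocol 7.2.5 and 7.2.6.1.3 on which papulo-pustular reactions must be declared. Which rule applies is for the sponsor to settle.

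The cost is a small CRF change, one tick per zone at visits already planned, and one more table; no visit or procedure is added. If the item is not adopted, Section 1.4 should at least say that papulo-pustular eruption is captured through AESI reporting. That removes the mismatch in wording but leaves ascertainment as it is.
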